9.2.4 Analysis of the key secondary efficacy outcome

The primary analysis of the key secondary endpoint will be performed in line with the key secondary objective and the treatment policy estimand. It will be analysed using the same methods as the primary endpoint.

9.2.5 Analysis of other secondary efficacy outcomes

Other secondary efficacy endpoints, all continuous in nature, will be analysed in a similar manner to the primary endpoint. Handling of intercurrent events will be in line with the treatment policy estimands as outlined in Table 9.2.

9.2.6 Analysis of exploratory efficacy outcomes

Descriptive methods will be used to summarise the exploratory endpoints. Those continuous in nature will be described using means and standard deviations, medians and their interquartile ranges, including full ranges. Binary endpoints will be presented with their frequencies.

9.2.7 Analysis of safety outcomes

The SAF will be used to perform all safety analyses.

If not otherwise stated, only device-related safety data will be considered in tables and figures. All safety data will be included in listings, with flags for safety data not considered to be treatment emergent.

Device-related AEs and SAEs will be tabulated by patient cohorts, SOC, and preferred terms. The events will also be summarized by maximum intensity, relationship to study treatment and outcome (premature discontinuation from treatment).

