8.9 Safety Assessments

Adverse events of special interest, serious adverse events and all device related non-serious and serious adverse events will be collected from the signature of the ICF until the participation of the patient is completed within the study. Serious Adverse Device Effects will be reported to the authorities.

In case an adverse event is suspected during the regular follow-up calls between the patient and the APA specialist, the APA specialist will contact the Investigator to enquire the investigation of the event and the assessment of severity and causality.

Detailed instructions on recording and reporting of serious safety incidents will be provided in the Study Procedure Manual.

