8.9.3 AEs of Special Interest

Given the objective of the study and the disease assessed, AEs of special interest will be collected irrespective of seriousness and relatedness. These AEs are typically ones concerning the motor functions of the patients and include but are not limited to falls, freezing of gait, rigidity, bradykinesia, dyskinesia, dizziness, stiffness, vertigo and in general the worsening of the disease.

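### By default the safety tables hold only device-related events, so apart from diary falls no by-arm summary of unrelated AESIs, nor (on the likelier reading) of unrelated SAEs, is planned

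*Protocol*

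**What the plan says.** Section 9.2.7 sets the display rule: unless stated otherwise, "only device-related safety data will be considered in tables and figures". The rest is kept, but as line data: "All safety data will be included in listings, with flags for safety data not considered to be treatment emergent". The one tabulation by group that it names is this: "Device-related AEs and SAEs will be tabulated by patient cohorts, SOC, and preferred terms".

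Collection is wider. Section 8.9 states: "Adverse events of special interest, serious adverse events and all device related non-serious and serious adverse events will be collected", with no restriction by arm. Section 8.9.3 adds that "AEs of special interest will be collected irrespective of seriousness and relatedness", and says that these events "include but are not limited to falls, freezing of gait, rigidity, bradykinesia, dyskinesia, dizziness, stiffness, vertigo" and worsening of the disease in general.

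The Safety Set (9.1) contains both randomised arms, less patients who do not start their assigned therapy. The safety endpoint (synopsis, Table 5.1) counts events related to the device or to study procedures. Falls also have an efficacy analysis: a negative binomial model on diary falls to week 12 (9.5.2), and another to week 24 as an exploratory analysis (9.5.3).

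**The concern.** The display rule reinstates the relatedness filter that section 8.9.3 deliberately removed at collection. Three features of this trial make the filter costly.

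- **Relatedness is judged open label.** The investigator decides it knowing the arm (6.1, 8.9.6).
- **The disease offers a ready alternative cause.** Under 8.9.6 an event put down to the underlying disorder counts as not related. Freezing, rigidity, bradykinesia and dizziness are easily attributed to Parkinson's disease, so an excess caused by home exercise could be classed as unrelated and drop out of the tables.
- **Exposure to the device differs by arm.** Both arms wear the insoles, but only the FeetMe arm uses the rehabilitation application during the randomised period (4.3).

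At stake is the objective of assessing the safety of the home-based programme. A randomised control group lets one ask whether the programme raises or lowers the frequency of these events. A table confined to device-related events gives that up. No data monitoring committee is planned (10.1), so the final tables are the main place where an imbalance would be seen.

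**Working it through.** The point concerns what is displayed, so most of the check is a comparison of sections.

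| Event type | Collected in both arms? | By-arm summary planned in the protocol? |
|---|---|---|
| Device-related AEs and SAEs | Yes (8.9) | Yes (9.2.7) |
| Falls | Yes, by diary and as an AESI (8.7, 8.9.3) | Yes, diary falls whatever their relatedness (9.5.2, 9.5.3) |
| Other AESIs judged unrelated | Yes (8.9, 8.9.3) | No, listings only (9.2.7) |
| SAEs judged unrelated | Yes (8.9) | Unclear; probably listings only (9.2.7) |

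**The SAE row.** In the tabulation sentence the device-related qualifier may govern AEs alone or both AEs and SAEs. The display rule stated just before it is general, which favours the second reading. The AESI row does not depend on this: unrelated non-serious AESIs are left out on either reading.

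**Asymmetry.** Section 8.9.4 ties an adverse device effect to an investigational device. Section 4.7 says that the control patients' insoles and Evaluation application, used to download monitoring data, are not regarded as investigational devices. Few control-arm events can then qualify as device-related, whatever the true frequency of motor events in that arm. The causality scale in 8.9.6 is worded for a medicinal product; I take it to mean the device.

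**Number of patients.** Section 9.4 assumes a difference of 14 cm/s, an SD of 27 cm/s, two-sided alpha 0.05 and 80% power. The two-sample t-test needs 59.36, rounded up to 60 per group, and 60 / (1 − 0.20) = 75. The plan's figures reproduce. They matter here only because they fix n = 75 per arm.

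**What an added table could show.** The protocol gives no AESI or SAE rates. Assume that a share p1 = 0.05 of control patients has an event and a share p2 of FeetMe patients, with n = 75 per arm and p̄ the mean of p1 and p2:

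power = Φ{ [(p2 − p1) − 1.96·√(2p̄(1 − p̄)/n)] / √[(p1(1 − p1) + p2(1 − p2))/n] }

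For p2 = 0.20, p̄ = 0.125. The first root is √(2 × 0.125 × 0.875 / 75) = 0.0540 and the second is √((0.0475 + 0.16)/75) = 0.0526. Then (0.15 − 1.96 × 0.0540)/0.0526 = 0.84, and Φ(0.84) ≈ 0.80.

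| Assumed FeetMe rate | Power |
|---|---|
| 10% | 21% |
| 15% | 53% |
| 20% | 80% |
| 25% | 94% |

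Only a large excess would be detected formally. The table would serve description and signal finding, not testing.

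**The case against.** A reader might infer that SAEs and AESIs are never compared between arms, or that no unrelated event will be tabulated. The protocol does not support either statement, for these reasons.

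- **The rule is a default.** It opens with a qualifier that allows exceptions, and section 9 leaves data displays to the SAP, which is not at hand. Further tables may be specified there. This stands. Even so, the protocol states a rule rather than leaving the matter open, and nothing in it makes the exception.
- **Falls are compared.** The first-named AESI is analysed by arm without a relatedness filter. This stands, and falls are excluded from the point.
- **Scales cover part of the ground.** MDS-UPDRS Part III, compared between arms at week 12, rates rigidity, freezing and bradykinesia; Parts I and IV touch on light-headedness and dyskinesia. This stands in part. They are scale scores covering limited recall periods or the examination itself, not counts of events over 12 weeks.
- **SAEs may be covered.** The tabulation sentence can be read as all SAEs, and the summary by relationship to treatment that follows would suit that reading. The exclusion of unrelated SAEs is therefore likely, not certain.
- **The tables match the endpoint.** The safety endpoint counts related events only. That shows consistency, but the endpoint shares the same one-sidedness.
- **A by-arm AESI table has its own bias.** FeetMe patients have weekly, then bi-weekly calls with the adapted physical activity (APA) specialist, at which potential adverse events are recorded (4.4) and passed to the investigator (8.9). The remote visits at weeks 4 and 8 list questionnaires only (7.4.2). The open-ended AESI definition adds to this. The objection stands as a limit on interpretation, mainly for non-serious events. It is a reason for a caveat, not for leaving the events untabulated.

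**Conclusion.** The point holds in limited form. By default, section 9.2.7 leaves unrelated AESIs other than diary falls without any by-arm summary and, on the more natural reading, unrelated SAEs too, although the trial collects both in both arms. The related-only table that remains is one-sided by the design of the trial.

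The number of events affected cannot be derived, because the protocol states no expected rates and no share judged unrelated. A reader might picture a doubling of AESIs that shows as no events in either arm. That would need every event to be judged unrelated, whereas 8.9.6 counts a possible relationship as related. It is a worst case, not an estimate.

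The conclusion assumes that no document outside the protocol already provides these tables. It is worth correcting, because the gap lies in the safety objective and the data needed are already being collected. It does not affect the primary analysis or the sample size.

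**What to change.** In section 9.2.7:

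1. Add descriptive tables of all SAEs and of all AESIs, by randomised arm and preferred term, irrespective of relatedness. Use the Safety Set and the 12-week primary intervention period, because patients may choose their treatment after Visit 3 (7.5).
2. Keep the device-related events as a second table.
3. State whether the device-related qualifier in the tabulation sentence applies to SAEs.
4. Add a footnote that the regular APA calls give the FeetMe arm more opportunity for non-serious events to be reported, and that at 75 patients per arm the tables are descriptive.

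The cost is one or two extra tables and a few lines of text. No new data are needed. The drawback is that an AESI excess in the FeetMe arm may partly reflect closer follow-up, so the table must be read with the footnote.

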9.3 Interim analysis

No interim analysis is planned for this study.

9.4 Determination of sample size

Sample size calculations have been performed using the software PASS 12.

The main objective of the RE-CONNECT study is to demonstrate the efficacy of FeetMe home-based rehabilitation program compared to conventional physiotherapy at Week 12 in PD patients. The primary endpoint is the change from baseline to Week 12 in gait velocity (cm/s) assessed during the 6 Minutes Walk-Test (6MWT).

The sample size computation is based on the study of Chris J Hass et al (Hass et al, 2014). aiming to determine the Minimal Clinically Important Difference (MCID) for the gait velocity in patients with idiopathic Parkinson's disease. In this study including 324 patients, MCID for gait velocity was classified as small, moderate and large with values of 6 cm/s, of 14 cm/s and 22 cm/s respectively (using a distribution-based analysis and the categorization defined by Cohen (Cohen et al, 1988.)). We aim to show that the Feetme rehabilitation procedure will allow to improve the change in gait speed at least in a moderate range in comparison with that in standard rehabilitation group and we set the difference to

be detected at 14 cm/s. In the Chris J Hass et al, the standard deviation of gait velocity was estimated at 27cm/s.

To detect a difference of 14cm/s between the two groups for the change in velocity with a standard deviation of 27cm/s for the change from baseline to Week 12 in gait speed (assuming a conservative correlation coefficient of 0.5 between the measures at baseline and at week 12), 60 patients per group are needed (two-sided Student's test, type I error of 0.05 and a power of 80%). To take into account a 20% rate of drop out for the measurement of the gait velocity at week 12 (based on previous studies using FeetMe Rehabilitation application on a similar population, 15% of lost to follow up and 5% of deaths or injuries), we plan to recruit 75 patients per group (a total of 150 patients).

9.5 Statistical analysis

Baseline characteristics will be described according treatment groups. Quantitative variables will be expressed as mean (standard deviation) or median (interquartile range) for non-Gaussian distribution. Categorical variables will be expressed as frequencies and percentages. Normality of distribution will be assessed graphically and using the Shapiro-Wilk test. The number of missing data will be also reported. No formal statistical comparisons will be done; clinical importance of any imbalance will be noted.

9.5.1 Analysis for the primary endpoint

The primary outcome (the change in the gait velocity between baseline and week 12, assessed during the 6 Minutes Walk-Test) will be estimated and compared between Feetme rehabilitation and conventional physiotherapy groups using the constrained longitudinal data analysis (cLDA) model proposed by Liang and Zeger including centre as random effect and adjusted for the covariable "already in a rehabilitation program" considered as stratification factor in the randomisation. We chose to use cLDA model in view of its potential advantages compared to the conventional ANCOVA model. First, the cLDA model provides more flexibility in handling missing data by including all observed data, which, in general, results in more power when testing treatment differences compared with the longitudinal ANCOVA model. Second, compared with the ANCOVA model, the cLDA model provides more appropriate confidence interval estimates, especially in the context of randomised clinical trials where proper randomisation ensures baseline balance. In the cLDA model, both the baseline and postbaseline values are modelled as dependent variables using a linear mixed model (using an unstructured covariance pattern model), and the true baseline means are constrained to be the same for the 2 treatment groups. The between-group mean differences in 12-week change in gait velocity will be estimated by the time-by-arm interaction as treatment effect size. The assumptions of the cLDA model will be checked. We will use the analysis of cDLA model residuals by examining graphically the normality of residuals (histogram and Quantile-quantile plot) and by using the Shapiro Wilk test. In case of strong departure from the normality assumptions (even after applying a logarithmic transformation), nonparametric analysis will be used as recommended by Vickers et al. (reference: 1) Andrew J Vickers. Parametric versus non-parametric statistics in the analysis of randomised trials with non-normally distributed data. BMC Medical Research Methodology 2005, 5:35 2) Conover WJ, Iman RL: Analysis of covariance using the rank transformation. Biometrics 1982, 38:715-724.); absolute changes between baseline and 12-week will be calculated and compared between the 2 treatments groups using nonparametric analysis of covariance adjusted for baseline values. The effect size will be assessed by Hedges's g (standardized differences) computed on rank transformed data with its 95% confidence interval (using the method based on noncentral Student distribution which is a corrected version of Cohen's d taking into account the sample size). A sensitivity analysis will be performed excluding from the FAS population patients who have a change in levodopa medication during the first 3 months. For this sensitivity analysis, we will use the same methodology as that described for the primary analysis.

9.5.2 Analysis for the secondary endpoints

The statistical method described for the primary objective will be used for the analysis of the following secondary endpoints:

- Change from baseline to Week 12 (Visit 3) in Stance Time Variability assessed during the 6 Minutes Walk Test (6MWT).
- Change from baseline to Week 12 (Visit 3) in the asymmetry of the swing duration assessed during the 6 Minutes Walk Test (6MWT).
- Change from baseline to Week 12 (Visit 3) in the MiniBESTest.
- Change from baseline to Week 12 (Visit 3) in MDS-UPDRS part III sub-score.
- Change from baseline to Week 12 (Visit 3) the results of the Parkinson Disease Questionnaire (PDQ-39)

The rate of falls during the primary intervention period will be compared between the 2 groups using a generalized linear model (GLM with log link function and negative binomial distribution) with the logarithm of duration of patient's follow up (censored at week 12) as offset variable. Effect size will be estimated by the relative risk ((Feetme rehabilitation versus conventional rehabilitation) and it's 95% confidence interval from the using GLM model.

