7.2.1.2 Randomisation

Eligible patients will be randomised using an Interactive Voice/Web Response System (IXRS) randomised either on the conventional physiotherapy or on the FeetMe arm in a 1:1 ratio. Randomisation will be stratified by the covariable "already in a rehabilitation program" and by study site. We will use a dynamic randomisation procedure by minimization using the Pocock and Simon method. Randomization will result in the assignement of the unique Patient ID, which will be used on all study-related documents pertaining to the patient. Any identification numbers that are assigned will not be reused even if the patient does not continue in the study.

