8.2 Medical History

A complete past medical history will be collected by the Investigator or appropriate site staff according to standard practice and recorded in the eCRF. This will include a history of all previous diseases and illnesses, those currently being treated until the time of the screening visit, as well as those which have any residual effects on the patient's health. Moreover, surgical history will be collected, including all invasive procedures the patient has undergone until the time of the screening visit. Previous falls should be recorded to the extent possible.

8.3 **Prior- and Concomitant Medication**

Details of all medication taken \leq 3 months prior to the Screening Visit or during the study until the EOS Visit will be collected by the Investigator or the site staff according to standard practice and recorded in the eCRF.

Patients are eligible if on stable treatment of PD medication for at least 30 days before screening. Major changes in PD treatment during the first 3 months of the study are not allowed. What is considered a major change is up to investigator judgement, nevertheless, in principle anything that would alter the gait of the patient is considered as such. For example, adaptation of the levodopa dose to maintain current level of ambulation is not considered a major change, while changing the posology of the

treatment (e.g.: switching from per os to parenteral), or introducing a new one would classify as one. Ideally no major changes should be issued during the whole duration of the study in other medication that can influence overall data interpretation either (e.g.: antidepressants).

In case major changes in concomitant medication are unuvoidable, either due to the worsening of a disease or a new disorder, it must be recorded in the eCRF specifying the reason (e.g.: worsening of a medical history, adverse event or as a new adverse event) and will be taken into account during analysis.

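### The negative binomial falls models omit both minimisation factors, so their standard errors are if anything too wide; the loss is probably small, and naming the covariates costs little

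*Protocol*

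**What the plan says.** - **Falls model.** Protocol section 9.5.2 lists five secondary endpoints that follow the primary method, then gives falls a model of its own: a "generalized linear model (GLM with log link function and negative binomial distribution". Log follow-up time, cut off at week 12, enters as an offset. It adds "Effect size will be estimated by the relative risk" with a 95% confidence interval. Treatment group and the offset are the only terms named. Section 9.5.3 repeats this for 24 weeks, directly after a mixed model for which the stratification covariable and centre are both named.
- **Allocation.** Section 7.2.1.2 states "We will use a dynamic randomisation procedure by minimization using the Pocock and Simon method". The factors are study site and whether the patient is already in rehabilitation.
- **Primary model.** Section 9.5.1 includes centre as a random effect and adjusts for the rehabilitation covariable.
- **Fall history.** Section 8.2 says "Previous falls should be recorded to the extent possible". It gives no look-back period, count or format, and no planned analysis uses the item.
- **General rule.** Section 9.2.5 says "Other secondary efficacy endpoints, all continuous in nature, will be analysed in a similar manner to the primary endpoint", and refers intercurrent events to Table 9.2. In that table, a missing week 12 value leads to use of the baseline data.

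**The concern.** Minimisation balances the arms on site and rehabilitation status. If either predicts falling, that balance removes some chance variation from the treatment comparison. A model that ignores the factors still counts this variation as error, so its standard error is larger than the design warrants. Prognostic value is plausible: section 4.1.2 cites a reduction in fall rate with rehabilitation, and section 6.1 expects geographical differences in physiotherapy practice.

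Falls is the first-listed secondary endpoint and is central to the rationale in section 4.2.2. No power is stated for it. Covariates named after the data are seen, in an open-label trial, would invite the charge of selective adjustment.

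Section 9.2.5 is a separate, smaller fault. A fall rate is a count over follow-up, and the diary has no baseline value, because section 7.3 puts baseline on the same day as screening. The Table 9.2 rule on missing week 12 values therefore cannot be applied to it.

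**Working it through.** **1. The plan's own figure.** Section 9.4 sizes the trial on gait velocity: difference 14 cm/s, SD 27 cm/s, two-sided 5%, 80% power. The normal approximation gives 2 × (1.960 + 0.842)² × (27/14)² ≈ 58.4, so 59 per arm. With the noncentral t, power is 0.7976 at 59 and 0.8042 at 60, so 60 per arm. 60/0.8 = 75. The stated 60 and 75 reproduce, but they say nothing about falls.

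**2. Inputs for falls.** The protocol gives none for this trial. Section 4.1.1 quotes, as background, an average of 60.5% of patients falling at least once a year and roughly 39% falling more than once. If yearly counts were negative binomial, P(0) = 0.395 and P(1) = 0.605 − 0.39 = 0.215. This is met by about 1.78 falls a year and dispersion k about 1.28: (1 + 1.28 × 1.78)^(−1/1.28) ≈ 0.395. Over 12 weeks that is 1.78 × 12/52 ≈ 0.41 falls per patient. Applying that k to a 12-week window, the higher rates below and a rate ratio of 0.5 are all assumptions.

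**3. Closed form.** SE(log rate ratio) = √[(1/n)(1/μ0 + 1/μ1 + 2k(1 − R))], where n = 60 per arm, μ0 and μ1 are the 12-week means, and R is the share of overdispersion that the covariates explain. For the first row with R = 0: √[(2.439 + 4.878 + 2.56)/60] = 0.406.

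| μ0, k | SE (power), R = 0 | R = 10% | R = 30% | R = 50% |
|---|---|---|---|---|
| 0.41, 1.28 | 0.406 (40%) | 0.400 (41%) | 0.390 (43%) | 0.379 (45%) |
| 1.0, 2 | 0.342 (53%) | 0.332 (55%) | 0.311 (61%) | 0.289 (67%) |
| 3.0, 3 | 0.342 (53%) | 0.327 (56%) | 0.294 (65%) | 0.258 (77%) |

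At R = 10% the SE falls by 1.5%, 2.9% and 4.4% in the three rows.

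**4. Simulation.** Negative binomial trials were simulated with 150 patients, 6 sites, balance within site by rehabilitation status, 20% partial follow-up and up to 300 runs per scenario. When the covariates were prognostic, adding the two minimisation factors cut the mean SE by about 1% to 4%; adding prior falls as well brought the total to about 4% to 21%. Two examples at rate ratio 0.5, in the order arm only, plus minimisation factors, plus prior falls:

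- 0.41 falls per 12 weeks, 50% of heterogeneity explained: SE 0.381, 0.369, 0.349; rejection 47%, 50%, 56%.
- 1 fall per 12 weeks, k = 2, 30% explained: SE 0.299, 0.295, 0.271; rejection 63%, 63%, 73%.

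Monte Carlo error is about 3 percentage points (√(0.5 × 0.5/300)). Some low-rate runs did not converge and were dropped, so these figures are approximate. Covariates with no prognostic value produced no material gain or loss.

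**5. In patients.** An SE cut of 1% to 4% equals 1/0.99² − 1 ≈ 2% to 1/0.96² − 1 ≈ 9% more patients.

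**The case against.** The strongest reply is that covariates of a secondary model outside the hierarchy are commonly left to the SAP. Section 9 promises full details there, and section 9.5.2 never says the model is unadjusted. This has weight: the SAP could add the terms without contradicting the protocol. But sections 9.5.1 and 9.5.3 name covariates where they are intended, and the falls model is fixed down to its link, offset and interval. Followed as written, it ignores the allocation factors.

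The contrast with the other endpoints should not be pushed too far. The non-parametric fallback in section 9.5.1 is described as adjusted for baseline values, with neither centre nor rehabilitation status, so it is not true that every continuous endpoint is adjusted for both.

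A reader might infer that the trial is giving up the equivalent of 9% to 25% of its patients, or many points of power. Simulations can produce that with 1 fall per 12 weeks, dispersion 1 and prior fallers falling 2 to 4 times as often, but none of these inputs is in the protocol. Most of that gain also comes from prior falls, which is not yet a usable covariate.

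A reader might also infer that sections 9.2.5 and 9.5.2 set two competing analyses for falls. They do not: section 9.5.2 leaves falls off the list of endpoints that follow the primary method and gives it a specific model, which governs. What remains is a wrong description and an intercurrent-event rule that cannot apply.

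**Conclusion.** The point holds as a modest, inexpensive improvement. The falls models at weeks 12 and 24 omit both factors used to allocate patients. If those factors are prognostic for falls, the standard errors are conservative. This direction carries no inflation of false positives.

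The size is conditional. The minimisation factors alone are worth about 1% to 4% of the standard error under assumed fall rates, dispersions and prognostic strengths, and nothing if they do not predict falls. A well-defined prior-falls covariate could bring the total to about 4% to 21%, again under assumed inputs. No single figure can be fixed from the protocol.

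The description in section 9.2.5 is wrong for falls whatever is assumed. Section 9.2.2 confines confirmatory testing to gait velocity and stance time variability, so the primary conclusion is untouched.

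**What to change.** 1. In sections 9.5.2 and 9.5.3, add the rehabilitation factor and centre to the negative binomial model, for example both as fixed effects given 6 sites. Fixed effects keep it an ordinary GLM; a random centre effect would make it a mixed model.
2. Add prior falls, for example any fall in a fixed look-back period (yes/no), provided the section 8.2 item is recorded in that form. There is no run-in diary to supply it otherwise.
3. State a simpler model to use if the adjusted one does not converge. This matters most at week 24, where group sizes are not controlled.
4. In section 9.2.5, drop the claim that these endpoints are all continuous. State that the rate of falls is analysed as in section 9.5.2 and that the Table 9.2 use of baseline data for a missing week 12 value does not apply to it.

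The cost is a few sentences, one definition for an item already collected, and seven extra parameters (five for site, one for rehabilitation, one for prior falls). No new assessment is needed.
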